15.2.1.2 Expedited Reporting of Adverse Events

The Medical Monitor should evaluate every AE to determine if (1) the AE meets the requirements for expedited reporting and/or (2) if the AE meets the criteria for a safety pause/prompt AE review (Section [15.2.2](#)). The Medical Monitor's contact information is provided in Section [16.2](#).

The study product for which expedited reporting is required is NOX66.

The Sponsor, or if designated, the CRO, will report all serious, unexpected, suspected adverse reactions observed in this clinical trial to the FDA in accordance with 21 CFR 312.32 (IND Safety Reports). SAE reporting procedures are provided in Section [16.1.2](#).

15.2.2 SAFETY REVIEWS

15.2.2.1 Initial Safety Evaluation

Enrollment will be stepwise starting with Cohort 1 (N=3). After 3 patients complete Cycle 1 and have taken at least 80% of the target number of doses, and completed all safety evaluations, all data will be reviewed by the SRC to determine if the next cohort can be enrolled. If no DLT was observed in a cohort of 3 patients, the next cohort of 3 new patients may be enrolled at the next higher dose level.

15.2.2.2 Safety Considerations for Dose Escalation

In addition to monitoring patient's safety throughout the study period, the Medical Monitor and Investigator will participate in the SRC meeting to assess cumulative safety data available on all

patients who had received at least 80% doses to determine whether dose escalation may occur according the prespecified rules in Section [8.1.1](#)

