----------------------	--

level. The previous dose level will then be considered for expansion to 6 patients in order to confirm that it is the MTD level. The MTD is defined as the dose level at which no more than 1 patient out of 6 experienced a DLT up to the end of Cycle 1. If in the first group at 800 mg daily (Cohort 1), 2 or 3 patients develop DLTs, then that dose level is considered to be the DLT level and 3 additional patients need not be tested at that level, but lower doses should be studied.

If no DLT is observed at 1800 mg (Cohort 3), dose escalation will be stopped. The proposed highest dose level (1800 mg) will be declared the MTD, and additional patients will be enrolled, if necessary, to ensure that a total of 6 patients are evaluated at this dose level.

The dose escalation scheme is presented in the following table.

Proposed Starting Dose and Dose Escalation Scheme for NOX66

Cohort	1	2	3
Increment	NA	50%	50%
Total daily dose (mg)	800	1200	1800
Daily regimen (mg)	400 BID	600 BID	600 TID

BID = twice daily, TID = three times daily. For each cohort, safety/tolerability and PK data will be collected on Days 1-2 and 7-8 for respective doses.

Assessment of toxicities and decisions about dose escalation and cohort expansion will be made by a Safety Review Committee, that will include at least one Sponsor representative participating investigators, and may also include a cardiologist or other outside consultants at the Sponsor's discretion.

Assessment of DLTs

Patients who withdraw in Cycle 1 for reasons other than safety or toxicity will be replaced. During the 7-day Monotherapy Period, any patient who develops a significant toxicity, as noted below, will be replaced.

For determination of DLT during Cycle 1, toxicity will be graded using the National Cancer Institute-Common Terminology Criteria for Adverse Events (NCI-CTCAE) Version 5.0. Any of the following, if judged to be associated with NOX66 alone or in combination with doxorubicin (i.e., possibly-, probably-, or definitely related to), will be considered a DLT:

- 1) Grade 3 non-hematological toxicities (excluding alopecia) with the following exceptions:
 - i. Grade 3 nausea/vomiting or diarrhea <72 hours with adequate antiemetic and other supportive care
 - ii. Grade 3 fatigue <1 week
 - iii. Grade 3 electrolyte abnormality that lasts 24 to 72 hours (Investigator's discretion for timeframe), is not clinically complicated

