8.3.5 EVALUABLE PATIENT

The criteria for determination of an evaluable patient for a dose escalation decision or determination of MTD, must include:

- Patient who experienced a DLT during the 21-day combination treatment cycle (Cycle 1) or
- Has not experienced a DLT and has taken at least 80% of the prescribed daily doses of NOX66 and completed all safety evaluations required in Cycle 1

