8.3.6 PATIENT REPLACEMENT

The following guidelines will be used to determine when a patient can be replaced

- During the Monotherapy period in the Dose Escalation part of the study, if a patient who is not tolerating the assigned dose of NOX66, may be replaced with another patient, following a joint decision between the Investigator and Medical Monitor. A maximum of 3 replacements is allowed in each dose level in the Monotherapy period.
- If any patient withdraws consent during Monotherapy period or during Cycle 1, he/she will be replaced with another patient.
- If any patient who has not taken at least 80% of the prescribed daily doses of NOX66 during Monotherapy period and Cycle 1, will be replaced with another patient.
- During the Dose Expansion Part, patients who have not completed at least 2 complete cycles of treatment, will be replaced with additional patients, until at least 12 patients have completed 2 cycles.

The recommended phase 2 dose (RP2D) may be defined as the highest dose of the combination administered if no DLTs are observed and the dosage form is acceptable to patients.

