14 STATISTICAL SECTION

14.1 SAMPLE SIZE

Up to 18 patients may be enrolled in the Dose Escalation part of this study, in cohorts of 3 or 6 patients at each specified dose. Patients must take at least 80% of their prescribed doses to be considered eligible for MTD evaluation. Sixteen patients will be enrolled in the Dose Expansion part of this study.

These sample sizes are not based on statistical considerations but are deemed sufficient to determine the MTD for and to describe the pharmacokinetic characteristics of this agent.

An expansion cohort of N=16 will allow a total sample size of up to 34 patients. If the expected response rate is 18% (6/34) for a hypothetical comparator and the expected response rate of NOX66 will be 24% (8/34) in the current NOX66-004 trial, this sample size ensures an 85% probability that the observed response rate of NOX66- will be greater than 18%.

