15.2.2.3 Safety Pause and Prompt AE Review

If a DLT occurs in 1 patient in a cohort of 3 patients at a given dose level of NOX66 + doxorubicin, then 3 more patients should be enrolled at that same dose level. If a DLT is not observed in the additional 3 patients, the next cohort of 3 new patients may be enrolled at the next higher dose level.

If DLT occurs in 2 patients in a cohort of 6 patients at a given dose level, then this dose level will be defined as the DLT dose level. All Investigators will be informed, no additional patient(s) will be enrolled at the DLT dose level, and dose-escalation will stop. No more than 6 patients should be enrolled at the DLT dose level.

The dose for the next cohort will be determined at the SRC review meeting to evaluate all the available safety (including AEs that are not DLTs).

When a DLT occurs, the site must immediately inform the CRO who will then inform the other sites that a DLT has occurred and evaluate if a second DLT has occurred at any other sites. If 2 or more DLTs occur at the same dose level, further enrollment of new patients at that dose level or higher across all sites will be suspended until the SRC meeting occurs to evaluate if the MTD has been exceeded. To be included in a dose-escalation decision or determination of MTD, an evaluable patient is defined as one who either experienced a DLT during the first 21-day treatment cycle (Cycle 1) or has not experienced a DLT and has taken at least 80% of the prescribed daily doses of NOX66 of the monotherapy period and the first 21-day treatment cycle and completed all safety evaluations required in Cycle 1.

Due to the potential for Cycle 1 discontinuations, patients withdrawing for reasons other than safety will be replaced.

When a dose escalation is stopped, the patients treated at lower doses can continue as planned.

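### Four statements of the 80% dosing condition (14.1, the synopsis, 8.3.6 and 15.2.2.2) make no exception for patients with a DLT, and so contradict the evaluability rule in 8.3.5 and 15.2.2.3

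*Combined protocol and SAP*

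**What the plan says.** Three rules state the 80% condition without qualification.

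- Section 14.1, repeated under sample size in the synopsis: "Patients must take at least 80% of their prescribed doses to be considered eligible for MTD evaluation".
- Section 8.3.6, third bullet, on any patient who "has not taken at least 80% of the prescribed daily doses of NOX66 during Monotherapy period and Cycle 1, will be replaced".
- Section 15.2.2.2, on the cumulative safety data that the Safety Review Committee (SRC) assesses: "patients who had received at least 80% doses to determine whether dose escalation may occur".

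Other passages set a different rule. Section 8.3.5 lists two alternative routes to being evaluable for a dose-escalation decision or the MTD. The first is "Patient who experienced a DLT during the 21-day combination treatment cycle (Cycle 1) or", with no dosing requirement. The second is for patients without a DLT, and only there does 80% apply. Section 15.2.2.3 repeats this two-route definition.

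On the scope of the review, 15.2.2.1 says that "all data will be reviewed by the SRC to determine if the next cohort can be enrolled". In that section 80% helps to set when the review happens, not whose data it covers. Section 15.2.2.3 has the SRC look at all available safety information, including adverse events that are not DLTs.

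**The concern.** Estimating the MTD of the combination is a primary objective (7.1), and it rests on counts of DLTs among 3 or 6 patients per level. The passages that decide who enters those counts should agree, above all on patients who stopped drug because of toxicity. Here they do not. A patient whose DLT interrupts NOX66 early in Cycle 1 is counted under two sections. Under three other rules, the same patient is ineligible, replaced or outside the cumulative review. A site, a data manager or an SRC member working from 14.1 or 8.3.6 alone could classify that patient differently from one working from 8.3.5.

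**Working it through.** **1. Who falls below 80%.** The plan's only figure on this point is the threshold itself. Inputs: 7 dosing days in the run-in and 7 in Cycle 1; 2 doses a day at 800 and 1200 mg, 3 a day at 1800 mg (Table 1).

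- Cycle 1 alone: 7 × 2 = 14 doses, 0.8 × 14 = 11.2, so 12 are needed. For three-times-daily dosing, 7 × 3 = 21, 0.8 × 21 = 16.8, so 17. A patient stopped at the end of Day 5 has 10/14 = 15/21 = 71%.
- Run-in plus Cycle 1, the basis worded in 8.3.6 and 15.2.2.3: 28 or 42 doses, with 0.8 × 28 = 22.4 and 0.8 × 42 = 33.6, so 23 or 34. After a complete run-in, a patient stopped at the end of Cycle 1 Day 4 has (14 + 8)/28 = (21 + 12)/42 = 79%, and at the end of Day 5 86%.

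So the conflict concerns DLTs that interrupt NOX66 in about the first four or five days of Cycle 1. A DLT appearing after Day 7, for example at the Day 10 to 14 nadir after doxorubicin described in 8.3.3, is unaffected if the NOX66 doses were taken.

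**2. Such a patient can arise under the plan's own rules.** Section 10.2.3 tells the investigator to delay NOX66 for a Grade 3 or 4 perineal or anal rash. A Grade 3 non-haematological toxicity at least possibly related to the combination is a DLT under 8.3.3, outside the listed exceptions. If it appears on Cycle 1 Day 3 and NOX66 is not resumed, the patient has at most 6/14 = 9/21 = 43% of the Cycle 1 doses, or (14 + 6)/28 = (21 + 9)/42 = 71% over both periods. That is below 80% on either basis.

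**3. How each section treats that patient.**

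| Section | Read as written |
|---|---|
| 8.3.5 | Evaluable: had a Cycle 1 DLT |
| 15.2.2.3 | Evaluable: same definition |
| 14.1 and synopsis | Not eligible for MTD evaluation |
| 8.3.6, bullet 3 | Replaced |
| 15.2.2.2 | Outside the cumulative escalation review |
| 15.2.2.1 | Data reviewed |

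**4. What one classification does to the decision (8.3.2).**

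- One early DLT among the first 3: counted, it is 1 of 3 and three more patients are enrolled at the level. Replaced by a patient without a DLT, it is 0 of 3 and the dose escalates.
- Two DLTs among 6, one of them early: counted, it is 2 of 6 and the level is declared the DLT dose level. With that patient replaced by one without a DLT, it is 1 of 6 and the level clears.

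The documents give no Cycle 1 DLT rate for the combination, so how often this would happen cannot be calculated.

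**The case against.** The strongest answer is that the sentences should not be read in isolation. Section 15.2.2.2 defers to the rules in 8.1.1, where the SRC decides once all safety data are available. Section 15.2.2.3 fixes both the scope of the review and the definition of an evaluable patient, and 8.3.5 gives that definition again. On this view the short 80% statements are shorthand for it. For Cycle 1 withdrawals, the synopsis and 15.2.2.3 tie replacement to reasons other than safety, and 11.2.2 to non-safety reasons or noncompliance, so the third bullet of 8.3.6 is most naturally about noncompliance. Section 15.2.2.3 also requires immediate notification of every DLT and suspends enrolment at two or more, with no dosing condition.

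Most of this stands, and it makes the intended rule fairly clear. It does not remove the conflict. Section 8.1.1 contains no definition of an evaluable patient that would restore the exception. The third bullet of 8.3.6 turns on doses taken and does not mention the reason. Section 14.1 states an eligibility condition outright.

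A reader might go further and infer that run-in toxicity is hidden, because "During the 7-day Monotherapy Period, any patient who develops a significant toxicity, as noted below, will be replaced" and such a patient is not in the Cycle 1 DLT count. The documents do not support that. DLT-grade run-in events are recorded in the eCRF (8.3.3). The Safety Set includes everyone given at least one dose (14.2). Adverse events are summarised by dose group and grade, and separately for onset before doxorubicin (14.3.4). Basing the MTD of the combination on Cycle 1 is a stated design choice (8.1.1).

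**Conclusion.** Wrong as written, minor. Sections 14.1 (with the synopsis), 8.3.6 bullet 3 and 15.2.2.2 contradict 8.3.5 and 15.2.2.3 on a patient with a Cycle 1 DLT who took less than 80% of NOX66, and 15.2.2.2 also conflicts with the full-data review in 15.2.2.1 and 15.2.2.3. The effect is confined to DLTs that interrupt NOX66 early, but in a cohort of 3 or 6 one such patient can change the escalation decision.

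A reader might infer that the SRC would disregard DLT patients. The documents do not show this: the evaluability definition, the full-data review and the non-safety limits on replacement all point the other way. The finding rests on the wording alone. The SRC charter (15.2.1) and the separate SAP (14.3.12) are not among the documents. They might restate the correct rule, but the protocol text would still contradict itself.

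**What to change.** - **14.1 and the synopsis:** insert *without a DLT* after *Patients* in the 80% sentence.
- **8.3.6, third bullet:** limit replacement for low dosing to patients without a DLT.
- **15.2.2.2:** describe the review population as *patients who received any NOX66 at the dose level*.
- **8.3.5 and 15.2.2.3:** no change; 80% remains the evaluability condition for patients without a DLT.

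The cost is a few words in four places, made as an amendment or administrative change under 17.7. The DLT definition, the MTD rule, the sample size and data collection are unchanged.

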15.2.2.3 Safety Pause and Prompt AE Review

If a DLT occurs in 1 patient in a cohort of 3 patients at a given dose level of NOX66 + doxorubicin, then 3 more patients should be enrolled at that same dose level. If a DLT is not observed in the additional 3 patients, the next cohort of 3 new patients may be enrolled at the next higher dose level.

If DLT occurs in 2 patients in a cohort of 6 patients at a given dose level, then this dose level will be defined as the DLT dose level. All Investigators will be informed, no additional patient(s) will be enrolled at the DLT dose level, and dose-escalation will stop. No more than 6 patients should be enrolled at the DLT dose level.

The dose for the next cohort will be determined at the SRC review meeting to evaluate all the available safety (including AEs that are not DLTs).

When a DLT occurs, the site must immediately inform the CRO who will then inform the other sites that a DLT has occurred and evaluate if a second DLT has occurred at any other sites. If 2 or more DLTs occur at the same dose level, further enrollment of new patients at that dose level or higher across all sites will be suspended until the SRC meeting occurs to evaluate if the MTD has been exceeded. To be included in a dose-escalation decision or determination of MTD, an evaluable patient is defined as one who either experienced a DLT during the first 21-day treatment cycle (Cycle 1) or has not experienced a DLT and has taken at least 80% of the prescribed daily doses of NOX66 of the monotherapy period and the first 21-day treatment cycle and completed all safety evaluations required in Cycle 1.

Due to the potential for Cycle 1 discontinuations, patients withdrawing for reasons other than safety will be replaced.

When a dose escalation is stopped, the patients treated at lower doses can continue as planned.

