8.1.1 DOSE-ESCALATION

For all dose escalation cohorts, there will be 7 days of monotherapy treatment with NOX66 followed by a 5- day washout period prior to the start of combination cycles of NOX66 and doxorubicin. The purpose of the monotherapy treatment is to evaluate the safety and tolerability of NOX66 when administered alone and as well as single and multiple dose PK of idronoxil.

The dose-escalation part of the study will include three planned Treatment Groups (800, 1200, 1800 mg daily) of 3 patients each. The first 3 patients will be entered at Dose Level 1 and will receive daily doses of NOX66 for 7 days. All of these doses, except for the 1800 mg have been evaluated in 2 previous clinical trials and have been relatively well tolerated as monotherapy for 14 days and in combination with carboplatin for 42 days.

After a rest period of 5 days and if no significant toxicities (DLT equivalent toxicity) have occurred, patients will enter the combination therapy part of the study which will consist of up to 6 x 21-day treatment cycles. Each cycle will consist of 7 days of NOX66 (at the assigned dose), doxorubicin (75 mg/m²) on Day 2 of the 21-day cycle (administered at approximately 1 hour after rectal application of NOX66) and a rest period of 2 weeks.

For the 800 mg and 1200 mg dose levels NOX66 will be administered twice-daily (BID) with a 400 mg or 600 mg suppository, respectively, and the 1800 mg dose level will entail administration of a 600 mg suppository three times daily (TID). In all cohorts, doxorubicin will be given initially at 75 mg/m² as an intravenous infusion over 15 minutes (or as per standard of care). This dose may be reduced to 60 mg/m², at the Investigator's discretion for unacceptable Grade ≥ 2 toxicity. A dose reduction of 50% is recommended if serum bilirubin is 1.2 -3.0 mg/dL prior to a cycle. If serum bilirubin is 3.1-5.0 mg/dL prior to a cycle, a 75% dose reduction of doxorubicin is recommended.

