8.1.2 COHORT EXPANSION

After the dose escalation part is completed, 16 patients will be enrolled into a Dose Expansion Cohort at the MTD of the combination. All patients will enter directly into 21-day combination cycles and will be given NOX66 therapy for 7 days and doxorubicin will be administered on Day 2. This will be followed by a 2-week rest period. Treatments will continue up to 6 cycles.

For both the Dose Escalation and Cohort Expansion groups, treatment will be terminated upon disease progression, unacceptable toxicity or a maximum of 6 cycles. In patients who develop Grade 3 or 4 toxicity determined to be related to NOX66, the Investigator may reduce the dose or frequency of dosing by one level so that the patients can remain in the study. Furthermore, all patients will be actively followed up for about 14 months after completion of Cycle 6 (including scheduled visits every 3 months) followed by telephone follow-up/chart review, for PFS and OS, at 15 and 18 months from the start of Cycle 1.

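### The 80% NOX66 compliance rule that decides who counts as DLT-free is worded inconsistently, and on its pooled reading 62-64% of Cycle 1 doses is enough

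*Combined protocol and SAP*

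**What the plan says.** The compliance condition appears in six sections of the protocol body, and again in the synopsis.

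- **Section 15.2.2.3:** a patient is evaluable with a Cycle 1 DLT. Without one, the patient is evaluable if he or she "has taken at least 80% of the prescribed daily doses of NOX66 of the monotherapy period and the first 21-day treatment cycle" and finished the Cycle 1 safety evaluations.
- **Section 8.3.6:** a patient who "has not taken at least 80% of the prescribed daily doses of NOX66 during Monotherapy period and Cycle 1" is replaced. One percentage again covers both periods.
- **Section 8.3.5** (the dedicated definition): the patient "has taken at least 80% of the prescribed daily doses of NOX66 and completed all safety evaluations required in Cycle 1". The lead-in is not mentioned. Cycle 1 attaches to the safety evaluations, so no dosing period is named.
- **Section 14.1:** "Patients must take at least 80% of their prescribed doses to be considered eligible for MTD evaluation". No period is given; the synopsis says the same.
- **Section 15.2.2.1:** the Safety Review Committee (SRC) reviews the data at this point: "After 3 patients complete Cycle 1 and have taken at least 80% of the target number of doses". The count is of target doses, not prescribed ones.
- **Section 15.2.2.2:** refers to receipt of 80% of doses, with neither a period nor a denominator.

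No section says which wording governs, or whether the 80% is pooled over the two periods or required in each.

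On reductions, Section 8.1.2 covers both parts of the study: after Grade 3 or 4 toxicity related to NOX66, "the Investigator may reduce the dose or frequency of dosing by one level so that the patients can remain in the study". It does not exclude Cycle 1. No section says how a patient reduced or held in Cycle 1 is counted at the assigned level.

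**The concern.** A compliance threshold for DLT evaluability normally serves to ensure that a patient called DLT-free was adequately exposed while DLTs were being counted. Here that window is Cycle 1 (Sections 8.3.2 and 8.3.3). Lead-in doses are not exposure in that window, so letting them offset missed Cycle 1 doses weakens the safeguard. Counting doses rather than milligrams of the assigned level can weaken it too.

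The missed doses need not be unrelated to toxicity. Section 10.2.3 calls for NOX66 to be delayed for certain rectal toxicities from Grade 2 upward. Grade 2 events are not DLTs under Section 8.3.3, and the plan does not say whether held doses remain prescribed doses.

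The rule feeds directly into the MTD, a primary objective, with only 3 or 6 patients per level. Reclassifying one patient can change a decision. Counting under-exposed patients as DLT-free makes a level look safer than it is. The opposite error, discarding a patient fully exposed in Cycle 1, costs a patient but does not itself push the MTD upward.

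**Working it through.** **Inputs.** For the lead-in, Section 8.1.1 states that "there will be 7 days of monotherapy treatment with NOX66 followed by a 5- day washout period". NOX66 is given on Days 1-7 of Cycle 1 (Table 2 footnote). Dosing is 2 times a day at 800 and 1200 mg and 3 times a day at 1800 mg (Table 1). Cycle 1 starts at the lead-in dose level (Section 10.2.2). The plan states no minimum Cycle 1 exposure, so there is no figure to reproduce.

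**Step 1: minimum Cycle 1 intake.** Doses per period = 7 x doses per day. Pooled need = 0.80 x two periods, rounded up. Cycle 1 minimum = pooled need minus a fully taken lead-in.

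| Regimen | Per period | Both periods | Pooled need | Cycle 1 minimum, pooled | Cycle 1 minimum, each period |
|---|---|---|---|---|---|
| BID | 14 | 28 | 22.4, so 23 | 23 - 14 = 9; 9/14 = 64.3% | 11.2, so 12; 12/14 = 85.7% |
| TID | 21 | 42 | 33.6, so 34 | 34 - 21 = 13; 13/21 = 61.9% | 16.8, so 17; 17/21 = 81.0% |

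If *daily doses* means dosing days, the pooled need is 0.80 x 14 = 11.2, so 12 days. That leaves 12 - 7 = 5 of 7 (71.4%) in Cycle 1. Required in each period, it is 6 of 7 (85.7%).

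**Step 2: the reverse case (BID).** Take 14/14 in Cycle 1 and 8/14 in the lead-in. The pooled figure is 22/28 = 78.6%, so the patient is non-evaluable under Section 15.2.2.3. If the 80% in Section 8.3.5 is read as Cycle 1 doses, the same patient is evaluable at 100%.

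**Step 3: a one-level reduction within Cycle 1.** Planned Cycle 1 NOX66 is 7 x 1200 = 8400 mg or 7 x 1800 = 12600 mg.

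- *1200 to 800 mg/day (600 BID to 400 BID).* From Day 2: (1 x 1200 + 6 x 800)/8400 = 71.4%. From Day 3: (2 x 1200 + 5 x 800)/8400 = 76.2%. From Day 4: (3 x 1200 + 4 x 800)/8400 = 81.0%. The dose count stays at 14/14 throughout, so neither prescribed nor target doses reveal the change.
- *1800 to 1200 mg/day (600 TID to 600 BID).* From Day 2: 3 + 6 x 2 = 15 of 21 doses, 71.4% of doses and of mg. From Day 3: 6 + 5 x 2 = 16 of 21, 76.2%. Against target doses pooled with a full lead-in, the Day 2 case is (21 + 15)/42 = 85.7%, which passes.

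**Step 4: effect on an escalation decision (illustration only).** Assume a true DLT risk of 30% at full exposure; this figure is not in the documents. With three fully exposed patients, the chance of 0/3 DLTs is 0.7^3 = 34%. Now let one patient take 9/14 of Cycle 1 doses.

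- All risk proportional to NOX66 taken: 0.30 x 9/14 = 0.193; 0.7^2 x 0.807 = 40%.
- Half the risk from doxorubicin and unaffected: 0.15 + 0.15 x 9/14 = 0.246; 0.7^2 x 0.754 = 37%.
- No risk dependent on NOX66: unchanged at 34%.

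**The case against.** A reader might infer that the protocol definitely pools the two periods, so that 62-64% of Cycle 1 doses is always enough. The documents do not establish that. Section 15.2.2.3 can also be read as 80% of each period, and Section 8.3.5 leaves the lead-in out. If the 80% applies to Cycle 1 or to each period, the minimum is 81-86%. This objection stands: the finding is that the wordings conflict, and that one natural reading of two of them gives 62-64%.

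A reader might also infer that any patient reduced in Cycle 1 passes as fully compliant. That is too broad.

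- Section 15.2.2.1 counts target doses, which would register the drop from TID to BID.
- The reduction in Section 8.1.2 requires Grade 3-4 toxicity related to NOX66. Most such non-haematological events are themselves DLTs, which makes the patient evaluable with a DLT. The excepted short episodes (nausea/vomiting, diarrhoea, fatigue, electrolytes) and blood-count events outside the DLT list remain.
- Scheduled Cycle 1 haematology and chemistry fall on Days 1, 9 and 16 (Section 11.4.2.4), so many laboratory triggers would surface after NOX66 dosing has ended.
- Patients enter Cycle 1 only after a lead-in at the same dose without DLT-equivalent toxicity (Section 8.1.1), and Cohort 1 has no lower planned level.
- The Table 2 footnote describes a fixed dose and regimen, and Section 8.3.4 places DLT-driven reductions in later cycles.

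The route is therefore narrow, but no text closes it.

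Finally, the SRC sees all safety data and may repeat a level or wait for more data (Section 8.1.1). Dosing times are recorded in diaries (Section 10.2.1). These are real safeguards, but no rule requires the SRC to weigh Cycle 1 exposure, and the evaluability wording decides who is put before it as DLT-free.

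**Conclusion.** The point holds as a conflict between definitions that affects a primary objective. The same patient can be evaluable under one section and replaced under another. On the pooled reading, with a full lead-in, a DLT-free patient needs only 9/14 (64%) or 13/21 (62%) of Cycle 1 NOX66 doses; with 80% in each period the figures are 12/14 and 17/21. Both sets are exact counts that depend only on the reading chosen.

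The dose-reduction gap is secondary. It matters for a non-DLT Grade 3-4 event that leads to a cut on Cycle 1 Day 2 or 3; from Day 4 the patient still receives 81% of the assigned mg.

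A reader might go further and infer that the MTD will be biased upward by a known amount. The documents do not support this. They give neither a DLT risk nor its dependence on NOX66 exposure, and all patients also receive doxorubicin. The shift from 34% to between 34% and 40% rests on the assumed 30% risk and one patient at the BID pooled minimum. This should be fixed, but it does not by itself invalidate the MTD determination.

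**What to change.** Replace the wordings in Sections 8.3.5, 8.3.6, 14.1, 15.2.2.1, 15.2.2.2 and 15.2.2.3, and in the synopsis, with one definition, and carry it into the SRC charter:

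1. A patient without a DLT is evaluable if at least 80% of the assigned-cohort NOX66 amount in mg for Cycle 1 Days 1-7 was taken, computed on Cycle 1 alone, and the Cycle 1 safety evaluations were completed. Held or reduced doses then count against the assigned amount.
2. Any lead-in compliance requirement is a separate criterion with its own threshold and stated consequence.
3. Patients reduced in Cycle 1 who still reach 80% remain evaluable and are flagged to the SRC; those below 80% without a DLT are replaced.

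The sponsor should also reconcile Section 8.1.2 with Section 8.3.4 and the Table 2 footnote on whether NOX66 can be reduced during Cycle 1. Which rule is right is not a matter for this review, and the definition above works either way.

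The cost is a few sentences. Occasionally one more escalation patient must be replaced, while some patients with full Cycle 1 exposure but a poor lead-in could be kept, depending on item 2. No dosing, delay or reduction rule changes. The definition should be settled before escalation decisions are made, since a later repair would mean reclassifying patients.
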